3.1.1 Design of the trial protocol

3.1.1.1 Objectives

Primary endpoints:

- Mitigate functional deterioration while hospitalization, by performing physical exercise with the FriWalk.
- Recover functional performance earlier after hospitalization.
- Validate FriWalk as a tool for measuring SPPB and gait speed (6m).

Secondary endpoints:

- To increase physical activity during hospitalization in Geriatric Acute Care and Orthogeriatric Units.
- Evaluate the influence of FriWalk in the onset of delirium during hospitalization.
- Evaluate the influence of FriWalk in the cognitive performance of the patients.
- Evaluate the influence of FriWalk in the affective sphere of the patients.
- Evaluate the influence of FriWalk in the quality of life of the patients.
- Evaluate the influence of FriWalk in the number of falls after discharge.
- Evaluate the influence of FriWalk in mortality.
- Evaluate the influence of FriWalk in the consumption of health resources after discharge.
- Evaluate FriWalk in terms of usability, satisfaction and acceptability.

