Physician.	 Pre-screening phase: the physician along with the clinical researcher will made a pre- selection of patients that could be participants in the pilot study. 	
Technical support.	- The technical support will develop training sessions about walker use. In addition, the walker maintenance will be carried out.	
Occupational Therapist.	 Exercises prescription. Validation of the FriWalk as diagnostic tool in Geriatrics Acute Care Unit. 	
FIB-HUG Professionals.	- They will perform the analysis data.	

A. VALIDATION OF THE FRIWALK AS A THERAPEUTIC TOOL:

Patients' selection will be made within 48 hours of initial hospital admission in the Geriatric Acute Care Unit, and in the Orthogeriatrics Unit after the stand permission by traumatology. These patients will be identified in both units through the admission list. Then physician and clinical researcher will check those participants who fulfil the inclusion and exclusion criteria. Next the participants will sign the informed consent and later the will be assigned by using a randomization process (through the www.randomizerd.org tool) to the control group or to the intervention group.

- **Control group**: the participants will receive the usual intervention, including rehabilitation programs if the participants need it during hospitalization.
- Intervention group: the participants will receive the usual intervention, including rehabilitation programs if the participants need it. In addition, we will provide them with the FriWalk as well as the exercises recommendations which prescribed by their physician and the Occupational Therapist.

Patients in the intervention group, who are hospitalized in Geriatric Acute Care or in Orthogeriatrics Unit, will dispose of the FriWalk at the time they have received authorization for walking by their doctor in Acute Care Unit, or for standing in Orthogeriatrics Unit until their discharge respectively.

The evaluations will be the same in both groups. When clinical researcher detects any alterations in the tests or questionnaires which might condition the patient's clinical management, the physician will be informed to take the appropriate measurements.

For both groups, data will be collected in five different moments; when patients' admission, at discharge, one month, three and six months after discharge.

In table 2 is describe pilot study in Geriatric Acute Care Unit and Orthogeriatrics Unit.

PHASE I: PRE-SCREENING.		
RESPONSABLE:	DESCRIPTION:	

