Clinical researcher. Physician.	Clinical researcher and physician will make an initial selection based on admission list (Orthogeriatrics Unit and Geriatrics Acute Care Unit). They will have to check that patients meet the inclusion and exclusion criteria a priori.	
PHASE II: SCREENIN	G AND RECRUIMENT.	
RESPONSABLE:	DESCRIPTION:	
Clinical researcher.	 Over pre-selected patients will be carried out different actions: Patients meet inclusion and exclusion criteria. Provide information about pilot study. If patients agree to participate in pilot study, informed consent will be provided and if they agree, then they will sign it. 	
PHASE III: RANDOMIZATION.		
RESPONSABLE:	DESCRIPTION:	
Person who does not participate in pilot study.	If patients agree to participate in the pilot study and sign the informed consent, they will be randomized and consequently assigned to control group or intervention group.	
PHASE IV: FIRST V	/ISIT (ADMISSION).	
RESPONSABLE:	DESCRIPTION:	
Clinical researcher. Occupational Therapist.	 Clinical researcher will carry out a patient examination composed of different tests and evaluations. Demographic and clinical data. Gait speed in 6 meters (Graham et al. 2008). SPPB (Short Physical Performance Battery) (Freiberger et al. 2012). Barthel Índex (Barthel and Mahoney 1965). Lawton and Brody (Lawton and Brody 1969). Confussion Assessment Method (Vasunilashorn et al. 2016). Semantic and Phonologic fluency (Mirra et al. 1991). MMSE (Folstein, Folstein, and McHugh 1975). Clock Drawing Test (Shulman 2000). 	

Table 2. Pilot study phases as therapeutic tool.

PHASE V RESPONSABLE: Technical support.	 Yesavage (Greenberg 2012). EuroQL-5D (Group 1990). Visual Analogue Scale for pain (only in Orthogeriatric Unit). Occupational Therapist will prescribe the physical exercises that patients should do. TRAINING. DESCRIPTION: After randomization, patients assigned to the
	intervention group, as well as their family and caregivers, will receive a training session about how to use the system.
PHASE VI:	FOLLOW-UP.
RESPONSABLE:	DESCRIPTION:
Technical support. Physician. Occupational Therapist.	During hospitalization, the technical support team will visit patient if he will need help for using the FriWalk. The physician and the Occupational Therapist will do the clinical follow-up.
PASE VII:	DISCHARGE.
RESPONSABLE:	DESCRIPCIÓN:

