Clinical researcher.	 New evaluation will be carried out at discharge moment with different tests and evaluations from admission. Demographic and clinical data. Gait speed (6 meters). SPPB (Short Physical Performance Battery). Barthel Índex. Lawton and Brody. Confusion Assessment Method. Semantic and Phonologic fluency. MMSE. Clock Drawing Test. Yesavage. EuroQL-5D. Visual Analogue Scale for pain (only in Orthogeriatric Unit). Length of admission. Adherence to treatment. We obtain this information by the FriWalk in the intervention group, and by questionnaires in the control group. Assistant level at discharge. System _Usability Test (intervention group).
PHASE VIII: VISIT 1 MC	ONTH AFTER DISCHARGE.
RESPONSABLE:	DESCRIPTION:
Clinical researcher.	 New evaluation will be carried out one month after discharge. Different test will be performed. Demographic and clinical data. Gait speed (6 meters). SPPB (Short Physical Performance Battery).

	/
	 Barthel Índex. Lawton and Brody. Confusion Assessment Method. Semantic and Phonologic fluency. MMSE. Clock Drawing Test. Yesavage.
	 EuroQL-5D. Visual Analogue Scale for pain (only in Orthogeriatric Unit). New admissions. Emergency visits.
	 Admission days in Emergency. Primary care visits Falls. Mortality. Assistance level at month 1.
PHASE IX: VISIT 3 MONT	
RESPONSABLE:	DESCRIPTION:
Clinical researcher.	 Last evaluation will be carried out. Demographic and clinical data. Gait speed (6 meters). SPPB (Short Physical Performance Battery). Barthel Índex. Lawton and Brody. Confusion Assessment Method. Semantic and Phonologic fluency. MMSE. Clock Drawing Test. Yesavage. EuroQL-5D. Visual Analogue Scale for pain (only in Orthogeriatric Unit). New admissions. Emergency visits. Admission days in Emergency. Primary care visits Falls. Mortality. Assistance level at month 1.
PHASE X: TELEPHON EVALUATIO	
RESPONSABLE:	DESCRIPTION:
Clinical researcher.	 We will make a call, 6 months after discharge: Barthel Índex. EuroQL. Mortality. Assistance level at month 1.
PHASE XI: DA	TA ANALYSIS.
RESPONSABLE:	DESCRIPTION:
FIB-HUG professionals.	At the end of the study, data analysis will be carried out using the information stored during the pilot study. Then, conclusions will be drawn about the use of the walker.

B. VALIDATION OF THE FRIWALK AS A DIAGNOSTIC TOOL.

Patients selected to validate the FriWalk as a diagnostic tool will be those who have been selected for therapeutic validation in Acute Care Geriatrics Unit setting.

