Geriatric Depression Test	This test is applied to explore if a given patient is suffering from depression. It consists in a set of 15 to Yes/No questions; a final score higher than 5 points may indicate depression; if it is higher or equal to 10 indicates depression with more accuracy.
EuroQoL-5D	This questionnaire is administered to evaluate the quality of life of the participants. It comprises 5 items: mobility, personal care, daily activities, pain and anxiety/depression.
Analogue Visual Scale for pain	This scale allows measuring intensity of pain. It consists on a 10cm line in which edges extreme expressions of pain are shown (no pain at all in the left hand-side, the unbearable pain on the right hand-side). Pain intensity is expressed in cm or mm.
Adherence to treatment	To evaluate if patients have committed to the prescribed therapy, a set of questions will be asked.
System Usability Test	This scale is administered to evaluate the usability of the system after being used. The final score ranges from 0 to 100.
Satisfaction	A questionnaire will be applied to evaluate patients' satisfaction after having used FriWalk.
Acceptability	Acceptability of FriWalk will be evaluated throughout a specific questionnaire.

The eCRF service will have, in general, the following functionalities:

- Access control by user roles: clinical researcher, CRA, administrator.
- Real-time verification of consistency in the input data.
- Security guaranteed by SSL-encrypted communications.
- Auditable activity log. All changes will be registered in such a way that the historic value of every field will be maintained. The author, date, time and reason of all changes will be indicated.

The service architecture will be based in a client-server paradigm. The client will consist in the following sections:

- Login: that will allow the start a session by introducing username and password. Depending on the user roles, different options will be available.
- Configuration: only available for the administrator. This section will allow the user to configure technical aspects of the service (URL, etc.).
- Administration: only available for the administrator. Assignation of a participant to a group.
- Form: available for the clinical researcher to upload information related to the development of the study.

The server:

- MySQL database where all the information will be stored.
- REST service.

- Privilege management.
- Data export service.

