10.8 Therapeutic Activities

Therapeutic activities are of two types: orthogeriatric activities and Therapeutic activities. 10.8.1 Orthogeriatric activities

Orthogeriatric activities are executed in the hospital (e.g., while the patient is healing from a trauma). For all orthogeriatric activities, the patient receives an invitation on the tablet, which can be accepted only if a caregiver is available for a direct supervision (the caregiver can be a paramedic, a relative or a close friend of the patient). If a caregiver is not available, either the exercise is simply skipped or it is prohibited to execute the exercise alone because being too dangerous. In the latter case, a mechanism of authorization/confirmation by the caregiver is adopted. The orthogeriatric activities supported by the FriWalk are the following:

- walk x minutes / one hour: in this scenario the walker reminds and invites the user to take a walk. The user exploits the robot as a standard walker to move wherever he wants, meanwhile sensors gather information about the distance covered by the user and the time of the walk;
- isometric/isotonic exercise: the walker is positioned in the environment for the correct detection of the user. The user is required to perform specific isometric exercises while the skeleton sense his/her performance.

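### Adherence is recorded by the FriWalk in one arm and by questionnaire in the other, so a between-arm difference in adherence cannot be separated from a difference in instrument

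*Protocol*

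**What the plan says.** Section 3.1.1.1 lists nine secondary endpoints for the clinical trial. The first is: "To increase physical activity during hospitalization in Geriatric Acute Care and Orthogeriatric Units".

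Table 2 in section 3.1.1.3 schedules adherence to treatment once, at discharge (Phase VII), and gives its source by arm: "We obtain this information by the FriWalk in the intervention group, and by questionnaires in the control group".

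Two other places describe the same assessment differently:

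- Section 3.1.1.3 A, after the description of the arms: "The evaluations will be the same in both groups".
- Table 5 (eCRF contents, section 3.1.3.1), adherence row: "To evaluate if patients have committed to the prescribed therapy, a set of questions will be asked". It mentions neither the FriWalk nor any split by arm.

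On what patients adhere to, section 3.1.1.3 A gives both arms usual care, with rehabilitation where needed, and adds for the intervention group: "In addition, we will provide them with the FriWalk as well as the exercises recommendations which prescribed by their physician and the Occupational Therapist". Phase IV of Table 2, the first visit after randomization, has no such restriction: "Occupational Therapist will prescribe the physical exercises that patients should do".

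On what the device records, section 10.8.1 says of the walking activity: "meanwhile sensors gather information about the distance covered by the user and the time of the walk". The same section has the device sense isometric and isotonic exercises through skeleton tracking.

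**The concern.** The rule in Phase VII concerns data collection, so a later analysis plan cannot repair it. Under that row no control patient has a device record, and none of the intervention patients is due to answer the questionnaire. If adherence is then compared between arms, any difference could come from the treatment, from the instruments, or from both. The absence of a difference would be just as ambiguous.

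This reaches one of the stated aims, because no other in-hospital item records how active patients were. Activity that is not recorded alike in both arms by discharge cannot be recovered afterwards.

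**Working it through.** The protocol gives no sample size, effect size or power for this aim, so there is no figure to reproduce. The check compares the relevant sections, followed by an illustration on assumed inputs.

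**1. Are instrument and arm separable?** Under Table 2, Phase VII, they are not:

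| | FriWalk record | Questionnaire |
|---|---|---|
| Intervention | yes | not scheduled |
| Control | none (no device) | yes |

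Only two of the four cells are filled. The arm indicator and the instrument indicator are the same variable, so a model containing both cannot be estimated.

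**2. Is there another in-hospital measure of activity?** The other items at admission and discharge in Tables 2 and 5 are:

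- function: SPPB, gait speed, Barthel, Lawton and Brody;
- cognition, delirium, mood, quality of life and pain;
- length of admission, assistance level, usability, satisfaction and acceptability.

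None records an amount of activity. Step counters appear only in the social trial (Tables 7 and 8). Adherence is therefore the only candidate. The link to the activity aim is inferred, since the protocol does not state it. Either adherence serves the aim and is confounded with instrument, or it does not and the aim has no measure.

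**3. Do the descriptions agree?** Section 3.1.1.3 A says the evaluations do not differ by arm, and for adherence Phase VII makes them differ. Table 5 has questions only, and Phase VII has a device record for one arm. Section 3.1.1.3 A adds exercise recommendations for the intervention arm alone, while Phase IV speaks of patients in general, so it is unclear what a control patient's adherence refers to.

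**4. What could an instrument difference do?** All inputs here are assumptions except the 0.05 level (section 3.1.4) and the 1:1 allocation (blocks of 4, section 3.1.1.3).

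Suppose there is no true difference, both sources are put on one scale, and they differ by b SD. For a two-sided z-test at 0.05 with n per arm,

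P(reject) = Φ(b/se − 1.96) + Φ(−b/se − 1.96), with se = √(2/n).

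For n = 30 and b = 0.5, se = 0.258 and b/se = 1.94, so P = Φ(−0.02) + Φ(−3.90) ≈ 0.49.

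| n per arm | b = 0 | b = 0.2 | b = 0.5 | b = 0.8 |
|---|---|---|---|---|
| 20 | 0.05 | 0.10 | 0.35 | 0.72 |
| 30 | 0.05 | 0.12 | 0.49 | 0.87 |
| 50 | 0.05 | 0.17 | 0.71 | 0.98 |

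The range of n is a rough guess from capacity. Two devices for six months give 2 × 182 = 364 device-days. At an assumed 7 to 14 days per patient that is 364/7 = 52 down to 364/14 = 26 intervention patients.

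In minutes, assume 30 min/day of true activity in both arms, recall at 70–150% of truth and a device log capturing 50–100%. Controls then read 30 × 0.7 = 21 to 30 × 1.5 = 45, and the intervention arm reads 30 × 0.5 = 15 to 30 × 1.0 = 30. The apparent difference runs from 15 − 45 = −30 to 30 − 21 = +9 min/day with no true effect. This range only restates its inputs. What it shows is that even the direction of the bias is unknown.

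**The case against.** The case on the other side has several parts.

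- **Adherence may not be meant as an outcome.** No section names it as the measure of the activity aim, and section 3.1.4 specifies no between-arm comparison of it. Table 5 ties it to commitment to the prescribed therapy, which is compliance and not amount of activity. As a process measure described within each arm, different sources matter less. This stands. A reader might infer that the activity aim is declared to rest on adherence and so compares instruments instead of treatments; the document does not say that.
- **The two sources are not as far apart as they may look.** A reader might infer that the questionnaire covers activity of any kind and that the device records only walking with it. Neither is supported. The questionnaire's content is not given beyond the reference to prescribed therapy. Sections 10.3 and 10.8.1 describe a platform that can also follow users and sense exercises. What remains is that activity away from the device is not described as recorded.
- **Table 5 is a short description.** It marks no arm restrictions anywhere, even for the usability test that Phase VII limits to the intervention group, so its silence on arm is weak evidence. If its questions are meant for everyone, a common instrument exists. That supports reconciling the sections, but Phase VII as written says otherwise.
- **The prescription conflict is an ambiguity.** Controls may have rehabilitation to adhere to, and the Phase IV row is damaged in the extracted text. It is worth clearing up, but it is a side issue.
- **The scale is limited.** One of nine secondary aims of a declared pilot is affected. This stands and sets the grade.

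**Conclusion.** The concern holds in this form: as Phase VII is written, a between-arm difference in adherence is fully confounded with the instrument, and the row conflicts with the statement that evaluations are the same in both groups and does not match the eCRF description. The conclusion needs no numerical assumption.

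The consequence for the physical activity aim follows by elimination. Adherence is the only in-hospital item that bears on it, and if it is not that aim's measure, there is none.

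A reader might infer that the trial's main therapeutic results are compromised. They are not: SPPB, gait speed and Barthel are scheduled alike in both arms. Nor should the rejection probabilities or the −30 to +9 min/day range be read as estimates of the bias. They rest wholly on assumed inputs, including that both sources yield a common scale, and carry no weight in the grading. This is a should-fix, best settled before enrolment.

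**What to change.** - Change the adherence line in Table 2, Phase VII, so that the same questions are asked in both arms at discharge. Add a short item on time walked and exercised by any means.
- Use only these answers for the between-arm comparison, and state whether they are the measure for the activity aim.
- Report the FriWalk log as a description within the intervention arm, and as a check on self-report there.
- Bring section 3.1.1.3 A, Phase VII and Table 5 into agreement on the source of adherence data. Reconcile section 3.1.1.3 A and Phase IV on who is prescribed exercise, so that it is clear what each arm adheres to.

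The cost is a few questions for every patient, of which the activity item is new, and one changed line in Table 2 with the matching eCRF fields. A common questionnaire does not remove all bias. Patients are 75 or older, and recall error may still differ by arm because only the intervention group gets feedback from the device. That should be stated as a limitation.

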3.1.1.3 Protocol

This is a prospective, randomized and blind pilot study.

The FriWalk validation as a therapeutic tool will be carried out in two clinical scenarios, one of them in geriatric acute care and the other in Orthogeriatrics Unit, because people usually use the walker in these units. On the other hand, the FriWalk validation as a diagnostic tool (SPPB and gait speed) will be carried out in Acute Care Geriatrics Unit, in those patients who have been recruited to FriWalk validation as a therapeutic tool.

The duration of the pilot will be one year, we will have two FriWalk during pilot. Recruitment time will be six months from the start of the pilot study.

Regarding the number of patients who will participate in the study, as FriWalk is a new technologic tool, which going to be included in model care in elderly people, we do not have previous data to evaluate the effect of the walker in clinical scenario. Hence, correct sample size cannot be calculated. So, we propose developing a pilot study in which all patients who meet inclusion and exclusion criteria and sign the inform consent will be included. The pilot study will last a year.

Patients' evaluations, in therapeutic tool scenario, will be carried out during hospitalization (in admission and discharge), one month after discharge, three months after discharge and six months after discharge. The last evaluation will be done by phone. A block randomization will be performed to ensure a balance between the control group and the intervention group in each setting. The block size is 4 (2 for control group and 2 for intervention group). In order to perform the randomization, we will always need that one of the FriWalk is free.

In the FriWalk validation as a diagnostic tool, the tests will be performed once there will not be a further follow-up.

In table 1 we will find described the professionals that participate in the pilot study as well as their responsibilities.

Table 1. Professionals.

PROFESSIONALS.		
RESPONSABLE:	COMPETENCES:	
Clinical researcher.	 Pre-screening and screening phases: check that patients meet inclusion and exclusion criteria. Give information to patients and caregivers about the pilot study and provide informed consent. The clinical researcher will carry out the evaluations during hospitalization, in discharge, and afterwards (one month after discharge and three months after discharge). Validation of the FriWalk as a diagnostic tool. 	

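### Falls and health-resource use after discharge are secondary endpoints with no stated end time, but the month 6 call does not ask about them, so 3 of the 6 planned follow-up months go unobserved

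*Protocol*

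**What the plan says.** Section 3.1.1.1 lists among the secondary endpoints "Evaluate the influence of FriWalk in the number of falls after discharge" and "Evaluate the influence of FriWalk in the consumption of health resources after discharge". Neither has an end time.

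Section 3.1.1.3 sets the timetable for the therapeutic part: "For both groups, data will be collected in five different moments; when patients' admission, at discharge, one month, three and six months after discharge". It adds, of the month 6 contact, "The last evaluation will be done by phone".

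Table 2 in the same section gives the items collected at each contact. The month 1 visit (Phase VIII) and the month 3 visit (Phase IX) both end with the same event list: "New admissions. Emergency visits. Admission days in Emergency. Primary care visits Falls. Mortality. Assistance level at month 1". For the month 6 contact (Phase X) the whole list is: "We will make a call, 6 months after discharge: Barthel Índex. EuroQL. Mortality. Assistance level at month 1".

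**The concern.** The two endpoints are open-ended, follow-up runs to month 6, and the last contact leaves out every item that would measure them. In practice, falls and resource use are measured to month 3, while mortality, Barthel and EuroQoL are measured to month 6. The Protocol does not say that the horizons differ.

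The gap lies in data collection, so an analysis plan cannot repair it. What is at stake is any difference between the groups in falls or service use that appears or persists after month 3, and the precision of both comparisons. Section 3.1.1.3 says no sample size can be calculated, and the risk table in section 3.1.2 rates too few participants as possible and major, so discarding observable follow-up is hard to justify.

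**Working it through.** **Items by contact (Table 2, Phases VIII to X)**

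| Item | Month 1 | Month 3 | Month 6 |
|---|---|---|---|
| Falls | yes | yes | no |
| New admissions | yes | yes | no |
| Emergency visits | yes | yes | no |
| Emergency admission days | yes | yes | no |
| Primary care visits | yes | yes | no |
| Mortality | yes | yes | yes |
| Barthel | yes | yes | yes |
| EuroQoL | yes | yes | yes |
| Assistance level | labelled month 1 | labelled month 1 | labelled month 1 |

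**Is there another source?** Section 3.1.2 says adverse events are communicated to the ethics committee. It gives no schedule and does not say that falls or admissions after month 3 are sought. Table 5 in section 3.1.3.1 has a resource-use row without time points and no separate row for falls. No diary or record review is described for the clinical trial. Nothing fills months 3 to 6.

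**Time unobserved.** (6 − 3)/6 = 0.50, that is 3 of 6 months.

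**Events unobserved.** The Protocol gives no event rate and no figure to reproduce, so the following is illustrative. Deaths and loss to follow-up are ignored.

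- Constant rate: the share of six-month events falling in months 3 to 6 is 3/6 = 50%. For Poisson counts the variance of a log rate ratio is inversely proportional to the expected events, so the standard error with three months of data is √(6/3) = 1.41 times that with six.
- Rate declining exponentially with half-life h months: with k = ln 2 / h, the share is s = (e^(−3k) − e^(−6k)) / (1 − e^(−6k)), and the standard error ratio is 1/√(1 − s).

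| Assumed half-life (months) | Share of events in months 3–6 | Standard error ratio |
|---|---|---|
| 1 | 11% | 1.06 |
| 2 | 26% | 1.16 |
| 3 | 33% | 1.22 |
| 6 | 41% | 1.31 |
| constant rate | 50% | 1.41 |

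**Overdispersion.** If counts vary between patients beyond Poisson, the variance of a group's log rate is roughly (1/n)(1/μ + φ), where μ is the expected count per patient and φ the overdispersion. Halving μ doubles only the first term, so the ratio is smaller than the corresponding Poisson figure.

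**Recall period.** The month 3 visit looks back 3 − 1 = 2 months to the previous contact. The month 6 call would look back 6 − 3 = 3 months.

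**The case against.** The best defence is that nothing is contradicted. The Protocol never promises six-month data on falls or resource use. Saying that data are collected at five moments does not mean every item is collected at each. The call also drops the physical performance, cognitive and mood tests, and Phase IX describes the month 3 visit as the last evaluation. That fits a full assessment to month 3 followed by a minimal call. The FriWalk is provided only until discharge, so a three-month horizon could be reasonable, and if its effect wanes, later months would dilute the contrast. Telephone recall over three months in patients aged 75 or over, whose cognition is itself a study outcome, is also weaker data.

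Much of this stands. A three-month horizon would be legitimate if stated, but it is not: the endpoints are open-ended, and the Phase IX description conflicts with the text that places the last evaluation at the telephone call. The dilution and recall points are reasons to report the first three months separately. They are not reasons to leave the later months unasked.

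A reader might also infer more than the documents support:

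- That named harms go unmonitored. Section 3.1.1.1 lists falls and resource use as secondary endpoints, not as harms, and mortality is collected at month 6.
- That deaths in months 3 to 6 can no longer be linked to a preceding fall or admission. No objective or analysis in the Protocol plans such a link.
- That the assistance level is lost after month 1. The item is listed at months 3 and 6, and the discharge list names discharge, so the label was evidently meant to change by visit. This is a copying slip, and assistance level is not a named endpoint.

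**Conclusion.** The point holds as a gap in the collection schedule for two secondary endpoints: three of the six planned follow-up months are unobserved for falls and all resource-use items. That half of the time is missing follows directly from Table 2. That half of the events are missing does not follow; it requires a constant rate. Under the assumed rate patterns the loss is 11% to 50% of six-month events, with a standard error ratio of 1.06 to 1.41, and less loss of precision if counts are overdispersed. These figures rest on assumed rates and on a treatment effect that is the same in both halves of follow-up. The Protocol sets no six-month target for these items, so this is a cheap improvement to the plan and not a breach of a stated commitment.

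**What to change.** In Table 2, Phase X, add falls, new admissions, emergency visits, emergency admission days and primary care visits since the month 3 visit. Ask the patient or caregiver, with the same wording in both groups, and provide the matching month 6 fields in the eCRF. Report falls and resource use as rates over observed time to month 6 or death, and show the month 0 to 3 result separately because the later data rest on longer telephone recall.

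As a clerical correction, change the assistance-level label to month 3 in Phase IX and month 6 in Phase X.

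The cost is about five questions in a call already planned, so a slightly longer call, and three-month recall against the two months between the month 1 and month 3 visits. Section 3.1.2 requires the sponsor's permission and ethics committee approval for protocol modifications. If the sponsor prefers to stop at month 3, writing that horizon into section 3.1.1.1 would remove the ambiguity, but the later events would remain uncollected.
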